13.5. Embedded Feasibility Study

An embedded feasibility study will assess recruitment and the use of NMP in recruited livers, to ensure that NMP is used where feasible. Due to logistical constraints (absence of trained staff, device already in use etc.), NMP may not be available for use in all cases, but lack of use may reduce the ability of the study to demonstrate an improvement in utilisation.

Go/no-go points at the end of 6-months are as follows:

- Recruitment of a minimum of 200 liver offers
- NMP utilisation in transplanted livers of > 50%, as a measure of protocol compliance. This will be assessed at a centre level, and poorly performing centres may be withdrawn from the study.

If recruitment or compliance with the intervention are outside these targets, recruitment strategies will be reviewed and a decision made as to whether to proceed.

No further interim analyses are planned.

13.6. The Level of Statistical Significance

Clinical Trial Protocol Template version 14.0

CONFIDENTIAL

© Copyright: The University of Oxford and Oxford University Hospitals NHS Foundation Trust 2018

The level of statistical significance will be set at a one-sided level of 2.5% for the primary outcome as superiority of NMP is required. For all other hypothesis tests a two-sided significance level of 5% will be used.

13.7. Procedure for Accounting for Missing, Unused, and Spurious Data.

Withdrawals from the trial after implantation will be documented, and a narrative analysis of withdrawals will be performed. Recipients withdrawing from the trial after implantation will be included in analysis using imputation methods for missing data, as described in the SAP.

The primary outcome will be available for all unused livers, and the majority of transplanted livers where the recipient attends a follow-up visit >10 months post-transplant or the liver fails at any point. It is anticipated very few patients will be lost to follow-up, but it is likely that not all measurements at all time points will be recorded for every recipient. Where data are missing from the registry for the study cohort at 3 and 12 months, attempts will be made to chase missing data.

Assuming that registry data are missing at random, with no effect of cohort on the probability of missing data, multiple imputation methods will be used to estimate missing variables. Sensitivity analyses will assess the effect of these assumptions.

13.8. Procedures for Reporting any Deviation(s) from the Original Statistical Plan

Any deviation from the original statistical analysis plan will require justification in the final study report.

13.9. Health Economics Analysis

The health economics aspects of the study are summarised here with details fully described in a separate health economics analysis plan (HEAP). The HEAP will be finalised prior to any analysis taking place.

The unit cost of NMP is greater than that of SCS, but it is hypothesised that the increased cost of the NMP technology will be (at least partly) offset by reduced costs elsewhere (e.g., shorter time on the transplant waiting list, reduced length of hospital and intensive care stay, fewer livers needed on average per transplanted patient); it is also hypothesised there may be health benefits (measured in terms of quality-adjusted survival) that may be balanced against any cost differences. The health economic analysis will incorporate these potential impacts and express the cost-effectiveness of NMP in terms of the incremental cost per quality-adjusted life year gained (the cost-effectiveness measure preferred by NICE) of NMP versus SCS.

A key feature of the health economic analysis, which differentiates it from the statistical analysis described above, is that for the health economic analysis the unit of analysis is the patient, whereas for the statistical analysis it is the liver.

We will generate evidence evaluating the cost, value for money and budget impact of NMP versus SCS from an NHS perspective that will be useful for NHS managers and commissioners when deciding whether or not to use the new technology. The analysis will include the following elements:

Clinical Trial Protocol Template version 14.0

CONFIDENTIAL

- (1) The cost of using NMP and SCS per liver. We will undertake a detailed micro-costing of both storage approaches, including staff and non-staff costs (both capital and consumables), valued using market prices. We will model the number of transplants anticipated per year for both the NMP and SCS approach, and multiply the respective costs of using NMP and SCS per liver by these numbers.
- (2) Costs associated with use of NHS services during the one-year following transplant per patient. These will be based on a combination of previously published data regarding the costs of care for liver transplant recipients in the UK (where available), as well as resource use data collected prospectively during the study using routine NHSBT data collection forms. These record data on length of initial ITU and hospital stay, use of renal replacement therapy, and total number of inpatient days and number of stays up to one year post-transplant. These data will be collected irrespective of whether the patient had NMP or SCS see below. Values will be monetised using national unit cost data from published sources.
- (3) Health outcomes in transplant recipients, measured in terms of quality-adjusted life years during the one-year follow-up period per patient. Health related quality of life, survival and QALYs per patient will be estimated from published data (where available), as well as being collected prospectively from patients recruited to the study (irrespective of whether or not they had NMP or SCS see below). EQ-5D-3L data (www.euroqol.com) will be collected pre-transplant, and at 3 and 12 months post-transplant. If the patient dies during the 12-month follow-up period they will be assigned a utility score of zero from that point onwards. Patient-specific utility profiles will be constructed assuming a linear relation between each of the patient's EQ-5D-5L scores at each follow-up point. The QALYs experienced by each patient from baseline to 12 months will be calculated as the area underneath this profile.
- (4) We will estimate the impact of NMP on the number of days and associated costs a patient spends on the transplant waiting list and assign a mean unit cost per day to this time. These costs may be derived from previously published data, or if unavailable from observing a cohort of patients on the waiting list during the course of the study.

The total costs of NMP and SCS will comprise the sum of (1), (2) and (4).

For items (2) and (3) we will group participating patients into four outcome categories (uncomplicated transplant with good function, complicated post-transplant course requiring total hospital stay >2 months in the first year, graft failure requiring re-transplantation, death) and we will calculate mean resource use and costs (item (2)) and mean QALYs (item (3)) over the one year period for all patients in each category, irrespective of whether or not they had NMP or SCS. The probability of ending up in each of the four outcome categories will be taken from study data, based on the primary and secondary outcomes of the trial and will be allowed to vary by whether or not the patent had NMP or SCS. Hence, this approach assumes that the mean costs and mean QALYs associated with each outcome category is the same irrespective of whether or not the patient had NMP or SCS; it also allows that the probability a patient ended up in each of the four categories may vary by whether or not they had NMP or SCS.

Cost-effectiveness will be calculated as the mean cost difference between groups divided by the mean difference in outcomes (QALYs) to give the incremental cost-effectiveness ratio (ICER) and incremental net monetary benefits (NMBs). We will subject the results to extensive deterministic (one-, two- and multiway) and probabilistic sensitivity analysis. The aim of the former is to identify the most important drivers of cost and cost-effectiveness; in addition we will undertake threshold analyses to identify the range of costs of NMP at which it is likely to be cost neutral and cost-effective. For the latter, we will apply recommended probability distributions around the parameter values and calculate confidence intervals Clinical Trial Protocol Template version 14.0

around the ICERs and incremental NMBs. These will also be used to construct cost-effectiveness acceptability curves, which will show the probability that each strategy is cost-effective for different values of the NHS' willingness to pay for an additional unit of outcome.

We will combine data on incremental costs with epidemiological data on projected numbers and undertake a budget impact analysis to evaluate what the total cost impact would be of rolling out NMP using a number of assumptions concerning adoption at individual NHS transplant centres and national levels.

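### Section 13.9 adds an annual (or per-liver) preservation cost to per-patient costs, although the declared unit of the cost-effectiveness ratio is the patient

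*Protocol*

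**What the plan says.** All statements are in Protocol section 13.9.

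- Unit of analysis: "for the health economic analysis the unit of analysis is the patient, whereas for the statistical analysis it is the liver".
- Item (1) is headed "The cost of using NMP and SCS per liver". After the micro-costing it continues "We will model the number of transplants anticipated per year for both the NMP and SCS approach", and its last step is to "multiply the respective costs of using NMP and SCS per liver by these numbers".
- Item (2) is "Costs associated with use of NHS services during the one-year following transplant per patient".
- Item (3), the QALYs, is per patient over the one-year follow-up.
- Item (4) estimates "the number of days and associated costs a patient spends on the transplant waiting list and assign a mean unit cost per day to this" waiting period.
- Total cost: "The total costs of NMP and SCS will comprise the sum of (1), (2) and (4").
- Ratio: "Cost-effectiveness will be calculated as the mean cost difference between groups divided by the mean difference in outcomes (QALYs").

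The opening of the section lists the hoped-for offsets to the cost of NMP: less waiting time, shorter hospital and intensive care stays, and fewer livers used for each patient transplanted. Its closing paragraph describes a separate budget impact analysis based on projected numbers. The section says that full detail is in a separate health economics analysis plan (HEAP), to be finalised before any analysis.

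**The concern.** Quantities can be added only if they are on the same unit. As written, item (1) ends as an amount per year for a whole strategy, while items (2) and (4) are amounts per patient, and no step brings them together. The sum is then the numerator of a ratio whose denominator is QALYs per patient.

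Cost-effectiveness for NHS commissioning is a secondary objective (section 6.2). The ICER, net monetary benefit, acceptability curves and the threshold price for NMP all rest on this sum. If the rule were followed to the letter, preservation cost would dominate and the offsets would hardly register. If item (1) were instead taken at its per-liver heading, the cost of livers preserved but not transplanted would drop out of the patient-level cost.

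**Working it through.** **Inputs from the protocol.** Eligible offers per year: 1242 (13.3). Utilisation with DUI above 0.27: 26% (5.2). Functional utilisation: 21.8% in controls, 31.4% anticipated under NMP, and 32.7% for a 50% improvement (13.3). Section 13.9 gives no unit costs.

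**Check of the volume base.** 1242 × (0.327 − 0.218) = 135.4, against the protocol's figure of around 135 extra functioning transplants a year. The 1242 is therefore the protocol's own annual base.

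**Annual transplants.**
- SCS: 1242 × 0.26 = 323.
- NMP: 1242 × 0.26 × (31.4/21.8) = 465. This assumes that the transplant rate rises in the same proportion as 12-month functional utilisation. With no uplift it stays at 323.

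**Reading A: item (1) as its last step defines it.** With c the cost per liver and N the transplants per year, the total for a strategy is c × N + (2) + (4). One pound on the cost per liver moves the total by N pounds, and one pound per patient on (2) or (4) moves it by one pound. The relative weight of (2) and (4) is therefore 1/N, that is 1/323 to 1/465.

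Illustration with assumed figures (NMP 10,000 and SCS 500 per liver, saving of 5,000 per patient on (2) plus (4)):
- Literal increment in (1): 465 × 10,000 − 323 × 500 = 4,488,500. The saving offsets 5,000/4,488,500 = 0.11%.
- Per patient, one liver per transplant: 10,000 − 500 = 9,500. The saving offsets 5,000/9,500 = 53%.
- Cost-neutral price of NMP, literal: (323 × 500 + 5,000)/465 = 358 per liver. Per patient: 500 + 5,000 = 5,500.

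Range, with NMP at 5,000 to 15,000, SCS at 500 and a saving of 5,000 to 20,000:
- Literal offset: from 5,000/(465 × 15,000 − 323 × 500) = 0.07% to 20,000/(323 × 5,000 − 323 × 500) = 1.4%.
- Per-patient offset: from 5,000/14,500 = 34% to 20,000/4,500 = 444%. Above 100% the cost difference changes sign.

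**Reading B: item (1) as its heading defines it.** The sum is c + (2) + (4), which is per liver plus per patient. The patient-level figure is k × c + (2) + (4), where k is livers preserved per patient transplanted. Illustrations of k from the protocol's background:
- Study of declined livers (5.4): 31 perfused and 22 transplanted, so k = 31/22 = 1.41.
- European randomised trial (5.3): discard 12% with NMP and 24% with SCS. If every discarded organ had been preserved, k = 1/0.88 = 1.14 and 1/0.76 = 1.32.

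On this reading (2) and (4) keep nearly their full weight, but k is missing. Fewer livers per transplanted patient is a lower k, so that named offset cannot appear in the sum. Reading A misses it too, because it multiplies by transplants and not by livers preserved.

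**The case against.** The strongest reply is that the section already tells the analyst the scale. It names the patient as the unit and calls the numerator a mean cost difference. The sentence on total cost can be read as listing which items count as costs and leaving out the QALYs. The annual multiplication looks like an input to the budget impact analysis, which the list also serves. Component scaling is ordinary HEAP content.

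Much of this stands. A careful economist would probably put item (1) on a patient basis. But the protocol is not silent here: it states a multiplication and a summation that do not fit its declared unit. Being able to guess the intent does not say how livers preserved and then discarded enter the patient-level cost.

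Three stronger inferences are not supported:
- *Item (1) is a national total.* It says per year and does not say national.
- *The preservation cost is wrong by a factor of several hundred.* That factor is essentially the annual volume under Reading A. It measures how far the literal rule departs from a patient basis, not an error in any reported figure.
- *The offsets cannot affect the ICER.* This is nearly true under Reading A and untrue under Reading B.

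A reader could also say that an all-annual basis, with annual costs and annual QALYs, would be coherent. It would, but it is not the unit the protocol declares.

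**Conclusion.** The point holds as a defect of definition. On either reading of item (1), the three cost items are not on one unit and do not match the per-patient QALYs. Under the literal reading, items (2) and (4) have about 1/323 to 1/465 of the weight of item (1). Under the per-liver reading, what is lost is the factor k, which lies between 1.14 and 1.41 in the protocol's own background figures and is unknown for this trial.

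The volumes rest on 1242 offers, 26% utilisation and the assumed uplift. The money figures rest on assumed unit costs and serve only as illustration. It is not shown that the eventual ICER will be wrong, because the HEAP was not available. The primary analysis is unaffected. The wording should be corrected because the commissioning results depend on it.

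**What to change.** In section 13.9, and in the HEAP to match:

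1. For the ICER and net monetary benefit, define item (1) as preservation cost per transplanted patient: cost per liver × livers preserved in that cohort, including those preserved and then discarded, divided by the number of recipients in that cohort. Add it to the per-patient means of (2) and (4) and set the total against per-patient QALYs.
2. Move the multiplication of cost per liver by annual volume to the budget impact paragraph and use it only there.

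The cost is about two sentences. No new data should be needed: section 9.7.2 already keeps preservation data for study livers declined after retrieval, and section 8.1 refers to livers retrieved for transplantation in the control cohort.

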14. DATA MANAGEMENT

A detailed Data Management Plan will be developed to outline the data management processing, data cleaning and QC procedures for the trial. The data management aspects of the study are summarised here with details fully described in the Data Management Plan.

14.1. Source Data

Source documents are where data are first recorded, and from which participants' CRF data are obtained. These include, but are not limited to, hospital records (from which medical history and previous and concurrent medication may be summarised into the CRF), clinical and office charts, laboratory and pharmacy records, diaries, microfiches, radiographs, correspondence and UK transplant registry data.

CRF entries will be considered source data if the CRF is the site of the original recording (e.g. there is no other written or electronic record of data). All documents will be stored safely in confidential conditions. On all trial-specific documents, other than the signed consent, the participant will be referred to by the patient trial ID, not by name.

14.2. Access to Data

Direct access will be granted to authorised representatives from the Sponsor, host institution and the regulatory authorities to permit trial-related monitoring, audits and inspections.

14.3. Data Recording and Record Keeping

Study liver and participant data will be entered onto the trial database designed and administered by the NHSBT CTU data management team using MACRO™, a commercially available FDA 21 Code of Federal Regulations (CFR) Part 11 compliant clinical trial database system. Following completion of analysis, the trial database will be archived in accordance with University policy.

The study team must keep the signed Informed Consent forms, all trial documentation and source documents collected during the trial in a secure location (e.g. locked filing cabinets in a room with restricted access). Direct access will be granted to authorised representatives from the Sponsor and host institution for monitoring and/or audit of the study to ensure compliance with regulations.

The participants will be identified by a unique patient trial ID in any database. Participant identifiers (e.g. NHS number) will only be stored where required for linkage to external data sources (e.g. NHS Digital, NHSBT). Individual participants will not be identified in the resulting publications and presentations from the trial.

All trial documentation will be retained for at least 5 years after trial completion or termination. In addition, the Investigator must not discard or destroy any trial specific materials unless otherwise instructed by NHSBT.

14.4. Use of registry data

The UK Transplant Registry will be the primary source of data about the donor and the organ retrieval. The primary source for the initial inpatient stay, 3- and 12-month and 5-year outcome data will be the UK Transplant Registry. Where primary or secondary outcome data are missing, we will use the electronic case report forms (eCRFs) to obtain missing data where recorded. For some outcomes data are only captured on the eCRFs for the prospective cohort, so the eCRFs will be the primary source for these outcomes. Linkage between trial and registry data will only be undertaken by statisticians working on the trial and registry identifiers will be removed from datasets after linkage has been undertaken. NHS Blood and Transplant Information Governance have conducted a Data Protection Impact Assessment, are satisfied that confidentiality and data protection measures are in place and approved the use of UK Transplant Registry Data for this study.

We will also request consent for linkage to other national data sources (e.g. NHS Digital, Office for National statistics) for the purposes of verifying resource use and clinical outcomes.

15. QUALITY ASSURANCE PROCEDURES

15.1. Risk assessment

The trial will be conducted in accordance with the current approved protocol, GCP, relevant regulations and standard operating procedures. A risk assessment and monitoring plan will be prepared before the study opens and will be reviewed as necessary over the course of the trial to reflect significant changes to the protocol or outcomes of monitoring activities.

15.2. Monitoring

Regular monitoring will be performed according to the trial specific Monitoring Plan. Data will be evaluated for compliance with the protocol and accuracy as defined in the trial specific Monitoring Plan. Following written standard operating procedures, the monitors will verify that the clinical trial is conducted and data are generated, documented and reported in compliance with the protocol and GCP.

15.3. Local Investigator and Site Personnel Training

All key site personnel must undergo relevant training in advance of the site initiation in accordance with Good Clinical Practice (GCP) guidelines. Such training will be documented.

All personnel involved in recruitment and data entry will also be trained in the use of the online recruitment and data collection tool by members of the clinical trials unit, and records of such training will be maintained.

15.4. Study Documentation

It is the responsibility of the local investigator to maintain complete, accurate and current study records. Each investigator will be provided with an investigator site file, online access to the case reporting system and other associated study specific documentation by the co-ordinating centre. Such records will be maintained during the course of the study and for up to 5 years following the date on which the study is terminated or completed.

15.5. Trial committees

There are a number of committees involved with the oversight of the trial. These committees are detailed below.

15.5.1. Trial Management group (TMG)

A TMG comprising the CI, other lead investigators, local principal investigators and members of the CTU. The TMG will be responsible for the day to day running and management of the trial. It will meet at least

four times a year, more often during set up and close down phases of the trial. At least one face to face meeting will be held each year.

15.5.2. Trial Steering Committee (TSC)

The role of the TSC is to:

- provide expert oversight of the trial
- maintain confidentiality of all trial information not already in the public domain
- make decisions as to the continuation of the trial
- monitor recruitment rates and advise the TMG on recruitment issues
- review and approve V1.0 of the protocol, and any substantial amendments
- review regular progress reports of the trial from the Trial team
- receive feedback from the DMC and consider their recommendations, including any ethical implications arising from their advice
- assess the impact and relevance of any accumulating external evidence
- monitor completion of Case Report Forms (CRFs) and comment on strategies from TMG to deal with problems
- monitor protocol deviations and advise the TMG on remedial action
- monitor any quality issues e.g. serious breaches and advise TMG on remedial action approve additional sub-studies
- oversee the timely reporting of trial results
- approve the statistical analysis plan
- approve the publication policy
- approve the main trial manuscript
- approve abstracts and presentations of results during the trial and on completion
- approve any requests for release of data or samples including clinical data and stored biological samples

The ultimate decision on continuation of the trial lies with the TSC.

